5.3. Behavioral Health Virtual Patient Navigation (BH-VPN) Program

The BH-VPN outlines the flow of patients from initial contact to their follow-up calls (see Appendix 1). In the existing ED workflow, patients are identified by a clinician in the ED as needing psychiatric evaluation and a referral is made to a tele-psych provider for a virtual consult. Patients who complete a telepsychiatric consult in the ED can be enrolled to either the control or intervention arm based on a randomization scheme that randomly allocates days that navigators are available. Psychiatrists are reminded through daily communication as to whether the BH-VPN program is available and the ED locations. The psychiatrist will make a recommendation to admit or discharge the patient. The ED physician will make the final decision on whether to admit or discharge the patient from the ED. Patients that have a discharge recommendation on days the program is available, will be offered the BH-VPN program. Enrolled patients are followed for up to 45 days.

If a discharge recommendation is made, a patient will be approached again by the navigator virtually for enrollment into the BH-VPN program. The patient has the option not to be followed by the navigator. Before discharge, the navigator will complete an initial virtual behavioral health assessment. The initial health assessment contains information such as preferred communication method, primary care provider, psychiatry provider, PHQ-9 screening, collateral resources, recent ED and hospital utilization, substance use disorder, medication barriers, appointment barriers, community resources, and crisis planning.

The follow-up assessments, which will occur during navigation phone calls at least weekly, may include information such as a suicide ideation safety screening, an appointment reminder, appointment barrier evaluations, medication obtainment follow-up, substance use disorder follow-up, PHQ-9 screening, supportive listening, psychoeducation, community resource follow-up, and additional crisis planning. Phone calls are weekly as standard care but may be more often depending on the individual needs of the patient. Appointments are dependent on a patient's specific needs and may be with a therapist or psychiatrist as well as other providers in the community such as primary care or referral to a community provider.

The Columbia-Suicide Severity Rating Scale (C-SSRS) helps identify whether someone is at risk for suicide, and the severity and immediacy of the risk. It also identifies level of support the person needs. The screening tool is administered during each phone contact to measure suicide ideation. If a patient is deemed actively suicidal, then the navigator will recommend transfer to mobile crisis, call 911 for a well-check, or call 911 to send the patient to the ED as per current standard of care.

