
Inclusion/ Exclusion Criteria
	
Inclusion:
 
 • Present to an ED at participating sites • Complete a telepsychiatric consult as captured in the electronic medical record • Complete a telepsychiatric consult during the navigator’s hours of operation • ≥ 18 years of age at time of ED encounter 
Exclusion:
 
 • No exclusions

Study Procedures
	
Patients are identified by a clinician in the ED as needing psychiatric evaluation and a referral is made to a tele-psych provider for a virtual consult. Patients who complete a telepsychiatric consult in the ED can be enrolled to either the control or intervention arm based on a randomization scheme that randomly allocates days that navigators are available. Psychiatrists are reminded through daily communication as to whether the BH-VPN program is available and the ED locations. The psychiatrist will make a recommendation to admit or discharge the patient. For patients that have a discharge recommendation on days that BH-VPN is available, patients will be offered the BH-VPN program. Enrolled patients are followed for up to 45 days. Each patient will receive the following core components:
 
 1. Introduction to the patient follow-up process prior to discharge 2. Follow-up evaluation within 72 hours by phone and weekly contact 3. Confirm that an in-person follow-up visit with an appropriate provider or clinician is scheduled. Where applicable, confirm in-network follow-up appointments are completed. 4. Ongoing assessment: substance use disorder, medication barriers, and appointment barriers 5. Assist with community resources, crisis planning, and supportive listening 6. Placement into an appropriate case management program, if needed. 
On days where the navigator is available, all patients who meet eligibility criteria will be considered exposed to the intervention; whereas, on days the navigator is not available all patients will be considered exposed to usual care.

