3. RATIONALE

To enhance the care of patients with a telepsychiatric consult, Atrium Health has designed a Behavioral Health Virtual Patient Navigation (BH-VPN) program. Navigators will monitor patients and assist with navigation through a weekly phone call after their index ED encounter for up to 45 days post ED discharge. The BH-VPN aims to improve patient outcomes through standardized approaches that leverage analytics and technology, while bridging care coordination. When a patient presents to a participating Atrium Health ED, those with a telepsychiatric consult completed on a randomized intervention day, during the hours of operation, are provided the option of participating in the BH-VPN program. A patient can choose not to receive care by a navigator post discharge.

The BH-VPN program includes the following key components: introduction to the patient follow-up process prior to ED discharge, follow-up evaluation within 72 hours by phone and weekly contact, confirmation that a follow-up visit is scheduled, where applicable confirm in-network follow-up appointments are completed with an Atrium Health provider, and placement into an appropriate case management program, if needed. There may be cases where patients are eligible to enroll in full case management programs based on their insurance and other criteria. For example, if a patient has Medicaid through Cardinal Innovations, a managed care organization providing local behavioral health care, and meets specific criteria, would no longer require navigation services. A patient's contact with the BH-VPN program ends after 45 days following ED discharge, or if there is a failure to contact, becomes enrolled with a case-management program, declines services, or the patient dies. For those patients enrolled in a case management program, then navigator will ensure the patient is in contact with case management program staff before ending contact with the patient.

This research project is a pragmatic, randomized evaluation of a quality improvement initiative which seeks to evaluate the effects of standardizing the use of a BH-VPN program among patients with a telepsychiatric consult. The outcomes evaluation of this intervention has been designed to integrate with routine care and minimize frontline staff burden by deploying an evaluation in a real-world setting.

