5.2. Randomization and Allocation

Randomization will be based on days the navigators are available to treat patients who've completed their telepsychiatric consult. Patients may be in the ED for multiple days. Their enrollment status depends on the day and time of their initial telepsychiatric consultation. Navigation will only be available for those patients whose consult occurs during intervention day/times. As part of the research design and rollout of this project, randomization will occur at the day level with the days being identified as intervention or usual care days for the duration of the study. Patients will accrue in both arms of the study during the navigators' days and hours of operation. Patients will not be accrued on days where the navigators are not potentially available such as weekends, nights, and holidays.

Block randomization will be used to assign days the intervention is offered. In each 7-day period (Monday through Saturday) there will be three days the program is offered and three days where the program is not offered. The program is not available to patients in the ED on Sundays. The hours of availability are 7AM to 11PM Monday through Friday and 7AM to 7PM on Saturdays.

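### The synopsis and Section 5.3 word the BH-VPN offer by the day of the discharge recommendation, while Section 5.2 and the Rationale tie arm and access to the day of the initial consult, so care can depart from the analyzed arm

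*Combined protocol and SAP*

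**What the plan says.** Two places fix access by the initial consult.

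- Section 5.2 (Randomization and Allocation): "Their enrollment status depends on the day and time of their initial telepsychiatric consultation", followed by "Navigation will only be available for those patients whose consult occurs during intervention day/times".
- Section 3 (Rationale): "those with a telepsychiatric consult completed on a randomized intervention day, during the hours of operation, are provided the option of participating" in the program.

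Two places word the offer by the discharge recommendation.

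- Section 5.3: "Patients that have a discharge recommendation on days the program is available, will be offered the BH-VPN program".
- Synopsis, Study Procedures: "For patients that have a discharge recommendation on days that BH-VPN is available, patients will be offered the BH-VPN program".

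Section 5.2 also says "Patients may be in the ED for multiple days", so the plan itself expects stays in which the two dates can differ. On the calendar, "there will be three days the program is offered and three days where the program is not offered" in each Monday-to-Saturday block, and "The program is not available to patients in the ED on Sundays". Under Section 5.3, psychiatrists get a daily reminder of whether the program is running and at which EDs. No mention is made of the arm of individual patients. The synopsis adds that eligible patients count as exposed on navigator days, but does not say which day counts for a stay of several days. Section 6.2 analyzes patients by assignment and adds a per-protocol analysis limited to those who received and adhered to their arm.

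**The concern.** The rule that decides who receives the randomized intervention is stated in two ways, and no section says which prevails when the dates differ. The synopsis and Section 5.3 are the workflow descriptions, and the only daily prompt they mention is about the day, not the patient.

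Take a patient first consulted on a usual-care Tuesday whose discharge recommendation comes on an intervention Wednesday. Section 5.3 read literally leads to an offer; Section 5.2 rules it out. In the reverse case, an intervention-arm patient goes without an offer. A Sunday recommendation after a Saturday intervention consult is not resolved anywhere: Section 5.2 gives the patient access by consult day and also says the program is unavailable that day.

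Three things are at stake:

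- The 45-day outcomes are diluted directly, because navigation is delivered to the wrong patients or withheld from the right ones.
- Index admission is affected only through a further step. The offer follows a discharge recommendation, so the offer itself cannot have changed that recommendation. Dilution arises if knowing that the program is or is not available on the later day influences a recommendation made or revised then.
- The per-protocol set is unclear, because care that follows Section 5.3 may breach Section 5.2.

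**Working it through.** **Step 1: the texts side by side.** If the recommendation is made on the day of the initial consult, all four statements give the same answer. They differ only if it is made or revised on a later day with a different program status. An overnight stay alone is not enough.

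**Step 2: the plan's own figures.** Section 6.1 assumes 60% admission under usual care and an 8-point reduction, so 52% under intervention. For a two-sided 0.05 test with 85% power, the usual formula is

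n per arm = [1.960 × √(2 × 0.56 × 0.44) + 1.036 × √(0.60 × 0.40 + 0.52 × 0.48)]² / 0.08² ≈ 690,

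or 1,380 in total. The stated 1,030 does not reproduce: 515 per arm gives about 73.5% power. That is a separate matter. It is the reason the size below is given in percentage points and not as a loss from 85% power.

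**Step 3: how often the next day has the other status.** Inputs are three program days in six and no program on Sunday (Section 5.2). Assumptions are equal volume on each of the six days and a delay of exactly one calendar day. Given one day's status, three of the other five days in the block have the opposite status, so Monday to Friday the next day differs with probability 3/5 = 0.60. Saturday is always followed by a day without the program.

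- Usual-care patient meets a program day: (5 × 0.60 + 0)/6 = 0.50.
- Intervention patient meets a day without the program: (5 × 0.60 + 1)/6 = 0.667.

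Equal volume is not critical. Saturday has 12 program hours and each weekday 16. Weighting by hours gives Saturday 12/(5 × 16 + 12) = 0.130. The two probabilities become 0.870 × 0.60 = 0.522 and 0.522 + 0.130 = 0.652. Their sum is 1.174 instead of 1.167.

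**Step 4: dilution.** Let f be the share of patients in each arm whose recommendation is made or revised on the next day. The documents do not give f. Assume staff follow Section 5.3 and that a patient meeting the other status takes on the other arm's admission rate in full.

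- Usual care: 60 − 8 × 0.50f
- Intervention: 52 + 8 × 0.667f
- Difference: 8 × (1 − 1.167f)

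| f (assumed) | Usual care crossing | Intervention crossing | Admission rates | Difference |
|---|---|---|---|---|
| 5% | 2.5% | 3.3% | 59.8% vs 52.3% | 7.5 points |
| 10% | 5.0% | 6.7% | 59.6% vs 52.5% | 7.1 points |
| 20% | 10.0% | 13.3% | 59.2% vs 53.1% | 6.1 points |
| 30% | 15.0% | 20.0% | 58.8% vs 53.6% | 5.2 points |

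**The case against.** The strongest reply is that Section 5.2 already governs. It limits navigation to patients whose consult fell in intervention time, and the Rationale repeats the rule. Section 5.3 describes one sequence of consult, recommendation and offer, so its day would normally be the consult day. On that reading the wording is loose and no crossover follows. This stands in part: the documents contain the right protection. They do not make it operational, because the workflow text and the daily reminder run on the day's availability and nothing directs staff back to the date of the first consult.

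Several stronger readings are tempting, and the documents do not support them.

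- A reader might infer that the intention-to-treat arms are misclassified. They are not: Sections 5.2 and 6.2 define them clearly.
- A reader might infer that every patient held overnight can cross over. Only those with a recommendation made or revised on a day of different status can.
- A reader might infer that a psychiatrist re-evaluates the patient and that bias in index admission is therefore established. No section describes a re-evaluation step, although calling the consult initial allows for later ones. Section 5.3 also leaves the final admission decision to the ED physician and the enrollment approach to the navigator. The effect on index admission is a possibility, not a finding.
- A reader might take the waits of 3 to 3.5 days in the Background as a guide to f. They concern patients awaiting state-hospital admission, so they do not measure it.

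The plan has some safeguards. The recurring Section 6 reports compare eligible with enrolled patients, but only in the intervention arm, so they would miss usual-care patients who received navigation. The per-protocol analysis depends on knowing which rule counts as adherence.

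**Conclusion.** The contradiction is in the current text and should be fixed. It threatens the separation between the arms in the care delivered; it does not affect the definition of the arms. The 45-day outcomes are exposed directly, and index admission only if availability on the later day influences the recommendation.

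How many patients would be affected cannot be derived from the documents. The range of 7.5 down to 5.2 points rests on an assumed share of 5% to 30%, a one-day delay, equal daily volume, staff following Section 5.3 over Section 5.2, and full adoption of the other arm's effect. It shows scale and does not predict a result. If staff follow Section 5.2, no usual-care patient receives navigation, and what remains open is the intervention-arm patient whose recommendation falls on a day without the program.

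**What to change.** 1. Reword the synopsis and Section 5.3 to agree with Section 5.2, so that the offer follows the arm fixed at the initial consult whatever day the recommendation falls on.
2. Add to the existing daily communication the arm of each patient still in the ED.
3. State how an intervention-arm patient recommended for discharge on a day without the program, Sunday included, is handled. This must be reconciled with the introduction before discharge in the synopsis and the navigator's assessment before discharge in Section 5.3; contact left to the next working day could come after the patient has gone home.
4. Use the consult, disposition and enrollment times already recorded to tabulate, by arm, recommendations made on a day of different status and patients whose access departed from their arm. State in Section 6.2 how these patients are treated in the per-protocol set.

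The cost is a wording amendment, a longer daily message, a small tabulation and occasional navigator enrollments on usual-care days. Any staffing cost of item 3 depends on the handling chosen and cannot be judged from the documents.

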5.4. Follow-up

Patients being treated in the BH-VPN program will receive a follow-up phone call within 24 to 72 hours from discharge, and then weekly for up to 45 days. A follow-up assessment is completed upon each phone call.

5.5. Patient Graduation from the BH-VPN Program

For the intervention arm, successful completion is defined as

- Enrolled for 45 days post ED admit date
- Enrolled in another Care Management program

For the intervention arm, failure to complete is defined as

- Unable to connect: 4 calls attempted over 12 days
- Death
- Declined services initially or after enrollment

5.6. Continuation of the Intervention

Participating ED sites may continue utilizing the BH-VPN program after the study period has ended.

6. DATA COLLECTION AND REPORTING

Patient demographics, comorbid conditions, and utilization will be obtained from the electronic medical record and billing systems. Data from the initial assessment and follow-up contacts will be stored in HealtheCare, a care management platform in Cerner. Data will be retrieved by an application specialist on the research team. Data may be retrieved retrospective to a patient's completion of the intervention or usual care arm of the study.

A bi-monthly report will be produced for the intervention arm. The report will be by ED site and overall.

- Count of patients meeting the inclusion criteria
- Count of patients with a HealtheCare account
- Count of patients enrolled in the BH-VPN program
- Patient list with their enrollment status in HealtheCare

A monthly report will be produced for the intervention arm. The report will be by ED site and overall. Report to be generated following the end of the previous month.

- Count of patients meeting the inclusion criteria
- Count of patients with a HealtheCare account
- Count of patients enrolled in the BH-VPN program

- Patient list with their enrollment status in HealtheCare

An Annual report will be prepared for the Duke Foundation measures.

6.1. Sample size analysis and statistical analysis

Given the preliminary data from our previous study, we will power the proposed study to detect at least an 8% absolute difference between hospital admission in the VIBRANT intervention and usual care groups. The usual care group is assumed to have a 60% inpatient admission rate based on prior data. There is 85% power to detect this reduction with a total sample size of 1,030 ($\alpha=0.05$) using a Chi-square test for independence. To account for the possible correlation among patients seen in the ED on the same day, we inflated the sample size by 10% assuming the average number of patients per ED per day is 2 with a 0.1 intra-class correlation coefficient (design effect = $1 + (2-1)*ICC$).¹⁴ Thus, the target sample size is $n=1,133$. The power was calculated using PASS 15 Power Analysis and Sample Size Software (2017). NCSS, LLC. Kaysville, Utah, USA, ncss.com/software/pass.

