1.1. Hypothesis

Index admission rates will be lower among patients who complete a tele-psych consult at an ED on days where the Behavioral Health - Virtual Patient Navigation (BH-VPN) program is available compared to patients who complete a tele-psych consult at an ED on days where the BH-VPN program is not available.

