4. SUBJECT AND SITE SELECTION

4.1. Accrual

As part of current care, patients are identified by a provider in the ED as needing psychiatric evaluation, and a referral is made to the telepsychiatric provider for a virtual consult. Patients are eligible to be included in analysis for the project if they meet the inclusion criteria and the telepsychiatric consultation occurs during potential BH-VPN program hours. We will accrue patient data for evaluation during a period starting in October 2019. Based on prior data, we estimate about 1,100 patients will complete a telepsychiatric consult in a 14-month period. Patients will not be accrued on days/times when the navigators would be not available (e.g. holidays).

Once a patient is in the intervention arm, the patient remains in the intervention arm until 45 days, or if there is a failure to contact (4 phone calls in 12 days), if the patient becomes enrolled with a case management program, declines services, or if the patient dies.

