6.2. Statistical analysis

Prior to analysis, descriptive statistics will be calculated to screen all variables for accuracy and to examine distributions.

All analyses will follow the intention-to-treat (“ITT”) principle, such that patients will be analyzed based on their assignment to the BH-VPN program or usual care. Balance in baseline characteristics between the groups will be assessed using Student’s t-test for normally distributed data, the Wilcoxon rank sum test for ordinal data or interval data that are not normally distributed, and the chi-square test for categorical data. Normality will be assessed using the Shapiro Wilk test and Q-Q plots.

The primary outcome, hospital admission (yes/no), is a binary dependent variable and will be compared between the BH-VPN and usual care groups using a generalized linear mixed-effects model with a logit link function. To adjust for correlation among patients seen on the same day and in the same ED, the model will include a random effect term for day nested within ED. The primary predictor in the model is an indicator for assignment to the BH-VPN program versus usual care. Additional baseline covariates will be included in the model if they are either strongly correlated with the dependent variable or show baseline imbalance between the two groups.

A similar approach will be used for the secondary outcomes to assess the patient-centric 45-day utilization rate, encounters with a self-harm diagnosis rate, and ED readmission rate. The models assessing these measures will be generalized linear mixed-effects models with a logit link, where utilization, diagnosis, or readmission, (yes/no) is the binary dependent variable. Independent variables in the models will be as described above for the primary analysis.

In addition, per-protocol analyses of the primary and secondary outcomes will be performed to evaluate the effect of BH-VPN program participation, in contrast to the ITT analysis evaluating the effectiveness of randomization to the program. The per-protocol analyses will include only subjects who received and adhered to the treatment (BH-VPN program or usual care).

Other binary outcome variables (e.g., frequency of patients active in the BH-VPN program) will be analyzed using descriptive statistics, unadjusted odds ratios, and 95% confidence intervals.

All tests will be two sided and the data will be analyzed using SAS Enterprise Guide 7.1 (SAS Institute Inc., Cary, NC, USA).

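### Section 6.1 claims 85% power at 1,030 patients for 60% versus 52% admission; its own inputs give about 73%

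*Combined protocol and SAP*

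**What the plan says.** Section 6.1 sets the target effect: "we will power the proposed study to detect at least an 8% absolute difference between hospital admission". It fixes the control rate: "The usual care group is assumed to have a 60% inpatient admission rate based on prior data". It calls the effect a reduction, in line with the hypothesis in Section 1.1 that admission will be lower when the program is available, so the comparison is 60% versus 52%. For a chi-square test at alpha 0.05 it then states: "There is 85% power to detect this reduction with a total sample size of 1,030". That number is raised by 10% for same-day clustering (2 patients per ED per day, ICC 0.1) to a target of 1,133.

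Three other statements bear on the calculation:

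- Section 6.2: "All tests will be two sided".
- Section 5.2, on each week's allocation: "there will be three days the program is offered and three days where the program is not offered". This supports roughly equal arms.
- Section 4.1: "Based on prior data, we estimate about 1,100 patients will complete a telepsychiatric consult in a 14-month period".

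**The concern.** A two-sided comparison of proportions near 0.5, with an 8-point difference and about 500 patients per arm, normally has power in the low to middle 70s, so 85% looked too high.

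This sentence is the only justification given for the size of the primary comparison. A reader of a null result would take it that an 8-point reduction had a 15% chance of being missed. Section 10 commits to a final report and a manuscript, where the figure would probably be repeated. If it is wrong, the trial is presented as more sensitive than it is.

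**Working it through.** **Inputs**

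- p1 = 0.60 and p2 = 0.60 − 0.08 = 0.52 (Section 6.1)
- Alpha 0.05 (Section 6.1), two-sided (Section 6.2): z = 1.960
- Power 85% (Section 6.1): z = 1.036
- Total 1,030, taken as 515 per arm. Equal arms is an assumption, based on the three-and-three day blocks in Section 5.2.
- Design effect 1 + (2 − 1) × 0.1 = 1.1 (Section 6.1)

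**Inflation step.** 1,030 × 1.1 = 1,133. This reproduces, so the error lies in the base figure of 1,030.

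**Attempt to reproduce 85% at 1,030.** With pooled variance under the null, the mean proportion is (0.60 + 0.52)/2 = 0.56.

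- A = √(2 × 0.56 × 0.44) = 0.7020
- B = √(0.60 × 0.40 + 0.52 × 0.48) = 0.6997
- Power = Φ[(0.08 × √515 − 1.960 × A)/B] = Φ[(1.8155 − 1.3759)/0.6997] = Φ(0.628) = **73.5%**

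Other methods agree: 73.7% with unpooled variance, 73.4% from the noncentral chi-square distribution (effect size w = 0.0806), and 73.0% from 400,000 simulated Pearson chi-square tests.

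**Sample size that 85% requires**

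- n per arm = [(1.960 × 0.7020 + 1.036 × 0.6997)/0.08]² = (2.1011/0.08)² = 689.8, rounded up to 690, so **1,380** in total
- With the plan's design effect: 1,380 × 1.1 = **1,518**
- 1,133/1,518 = 0.746, so the target is about 25% short
- Even 80% power needs 1,208 before inflation

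**After clustering**

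- Target: 1,133/1.1 = 1,030 effective patients, power 73.5%
- Forecast accrual: 1,100/1.1 = 1,000 effective patients, power Φ(0.590) = 72.2%

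**Detectable difference.** Solving the power formula for 85% at 515 per arm gives 0.0927, that is, 60% versus about 50.7%.

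**Alternative readings**

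| Reading | Power at 1,030 unless stated | Total for 85% |
|---|---|---|
| Two-sided, 60% vs 52% (as documented) | 73.5% | 1,380 |
| Two-sided with continuity correction | – | 1,430 |
| One-sided 0.05 (or two-sided 0.10) | 82.8% | 1,106 |
| Two-sided, 1,133 patients, clustering ignored | 77.5% (at 1,133) | 1,380 |
| 2:1 or 1:2 allocation | 68–69% | – |
| 1,030 per arm | 95.6% | – |
| Two-sided, 60% vs 68% | 76.3% | 1,290 |
| One-sided, 60% vs 68% | 84.9% | 1,034 |

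Only the last row matches the stated pair of 85% and 1,030. It needs a one-sided test, against Section 6.2, and an increase in admission, against Sections 1.1 and 6.1. It may show how the software was run, but that is inference.

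**The case against.** The arithmetic for 60% versus 52% is hard to dispute. The stronger objections concern how much weight it should carry.

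- **One combination does reproduce the figure.** A one-sided test of 60% versus 68% gives 84.9%. This points to a data-entry slip, but it contradicts two stated inputs and so does not make the sentence correct.
- **73.5% is a planning figure.** It depends on an assumed ICC and cluster size. With negligible clustering, 1,133 patients give 77.5%; with stronger clustering, power falls below 73.5%. The analysis itself is a mixed logistic model with possible covariates, not a chi-square test. This stands as a caution. It does not rescue the claim, because Section 6.1 makes it for the chi-square test and names no gain from covariates.
- **The 1,100 figure is a rounded forecast.** It is only 3% below target, and no accrual end date is fixed. This also stands: the 72% is conditional on accrual stopping there, and the conclusion does not need it.
- **No estimate or test is biased.** Results will be given as odds ratios with 95% confidence intervals, which show what a null result excludes, and no decision rule depends on the 85%. That limits the harm, but the stated power is still wrong.

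**Conclusion.** The concern holds. Under the plan's stated inputs (60% versus 52%, two-sided alpha 0.05, chi-square test, total 1,030) power is 73.5%, which is 11.5 points below the stated 85%. The corresponding type II error is 26.5% rather than 15%. The gap is far larger than the spread of under one point between calculation methods.

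The result rests on equal allocation, and the unequal ratios tried lower the power further. For the target of 1,133 it also rests on the plan's own design effect of 1.1. The error affects the justification of the sample size and the reading of a null result; it does not affect the validity of the analysis.

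**What to change.** Correct Section 6.1 and keep the enrolment target. Suitable wording: with 1,133 patients (an effective 1,030 at a design effect of 1.1), equal allocation and two-sided alpha 0.05, the trial has about 73% power to detect a reduction from 60% to 52%, or 85% power to detect a difference of about 9.3 points (60% versus 50.7%). Add that power for the 8-point difference would be about 72% if accrual stops at the forecast 1,100. State that the test is two-sided in Section 6.1 itself.

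The cost is a wording change and a less favourable power statement, with no extra patients. If the sponsor wants to keep 85% power for 8 points, the target has to rise to about 1,518, which is 385 more than now planned. If other inputs were used in the software, they should be stated, because the printed ones do not give 85%.
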